## 2.0 Objectives

# 2.1 Primary Objective

H1: Participation in VR active video gaming incorporating explicit and implicit learning, feedback and knowledge of results, and knowledge of performance motor tenets will lead to increased postural control, as reflected by improved static and dynamic balance. This hypothesis will be tested by Specific Aim 1: to assess the effect of a short-term (3 days/week for 2 weeks) VR active video gaming intervention on static balance, versus traditional balance training exercises, in youth with ASD.

H2: Participation in VR active video gaming incorporating explicit and implicit learning, feedback and knowledge of results, and knowledge of performance motor tenets will reduce the deviation in the spatiotemporal parameters of the gait due to increased dynamic balance and improved motor coordination. This will be tested by Specific Aim 2: to assess the effect of a short-term (3 days/week for 2 weeks) VR active video gaming intervention on spatiotemporal parameters of gait, as a measure of dynamic balance, versus traditional balance training exercises, in youth with ASD.

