# 3.0 Outcome Measures/Endpoints

# 3.1 Primary Outcome Measures:

- 1. High resolution pressure mat: Static balance will be objectively measured using an HR Mat pressure mat (Tekscan Inc.). The center of pressure will be measured at 100Hz using the center of pressure coordinates by inbuilt software. The area of the postural sway and direction of the sway will be measured as indicators of static balance with participants standing on the pressure mat with hands at their side under 2 conditions: eyes open and eyes closed for 30 seconds each condition. A member of the research team will stand beside the participant and provide balance support as needed.
- 2. Qualisys Motion Capture system: Step length, stride length, step-width, double support period, cadence and velocity are the gait parameters that will be measured as indicators of dynamic balance using Qualisys motion capture system. The

Qualisys motion capture system will be used to assess gait as a measure of dynamic balance. The system is composed of 13-infrared cameras that capture light reflected by passive markers at a frequency of 100 Hz. It is a reliable and a valid tool for gait assessment. The biomechanical model of feet will be constructed using Visual 3D software for gait analysis. Participants will wear the same sneakers/sports shoes for each assessment. Nine markers will be placed bilaterally (18 total) at the following points: distal aspect of the great toe, 1st metatarsal, 5th metatarsal, top of the foot, medial malleolus, and lateral malleolus, proximal heel, distal heel, and lateral heel. A comfortable walking speed for each participant will be recorded using a stopwatch to measure the time it takes them to walk back and forth on a 15-meter-long-platform 3 times and the average of the 3 trials will be calculated. Participants will then walk at the same speed at least 5 times or until the entire gait cycle is captured by the infrared camera system twice. Gait cycle is defined as heel-strike to heel strike on the dominant foot. A couple of practice trials will be performed to ensure understanding of the procedure and verbal prompting will be used to remind the participant to walk typically. Biomechanical models of feet will be constructed using Visual 3D software for gait analysis. If the participant is unable to perform this assessment as described, it will be rescheduled up to two times before study dismissal.

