# 3.2 End points:

- 1. Primary endpoints: Reduction in PBS total score by 3.7 points. This is in accordance with the MCID range reported by Chen et al, 2013 as 3.66-5.83 for PBS in children with neuromotor impairments.
- 2. For static balance: 1) reduction in the sway area of 95% confidence ellipse for center of pressure, 2) reduction in mediolateral direction of the postural sway.
- 3. For dynamic balance: Reduction in 1) step width, 2) double support period. Increase in 1) step length, 2) Cadence, 3) Gait velocity
- 4. Secondary endpoints: Safety.

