# Flow diagram for randomized, controlled trial

## 6.0 Enrollment/Randomization

40 school age children and youth with ASD will be recruited through local community agencies (e.g., schools, churches, and rehabilitation centers), social media platforms (e.g., Facebook and Reddit) and direct contact. Participants will be divided into 2 groups based on their age such as, group 1: 7-14 years and group 2: 15-22 years. Co-PI will allocate participant based on the coin flip such that heads = intervention group and tails = control group. The next participant in the same age range (range 1: 7-14 years, range 2: 15-22 years) will be assigned to the other group.

The process will continue till there are 10 participants in each age range for each intervention and control group (total n = 40).

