# 11.0 Statistical Considerations

According to prior research study examining the similar paradigm using Xbox games (Ghobadi et al. 2019), we predict the medium effect size (f=0.25) to detect significant changes within groups, between groups and effect of timepoint on static and dynamic balance. Power analysis

(using G\*power 3.1.9.7 software) indicates 14 subjects in each group to have 0.8 power to detect this effect (alpha 0.05). To account for the likelihood of attrition and noncompliance, total 40 participants are being recruited. Data from participants who engage in all the intervention sessions will be included in the analysis.

SPSS (Statistical Package for the Social Sciences) and MATLAB will be used for processing and analyzing the data. Participants demographic and health characteristics will be compared using paired sample t-tests. Intention to treat analysis will be used for addressing effects of treatment or control on static and dynamic balance. The dependent variables for static balance include: 1) sway area of 95% confidence ellipse for center of pressure(mm²), 2) direction of center of pressure sway as anteroposterior and mediolateral (mm). The dependent variables for dynamic balance are: 1) step length (m), 2) stride length (m), 3) step width (m), 4) double support period (sec), 5) cadence (steps/min) and 6) gait velocity (meters/min). Total PBS score will be dependent variable for both static and dynamic balance.

Two-way repeated measures ANOVA (analysis of variance) will be used to determine 1) within intervention and control group, for assessing the main effect of group, 2) between intervention and control group for assessing main effect of time, and 3) between - within interaction for assessing the interaction term. Statistical significance will be declared if  $p \le 0.05$  (two-tailed).

[name] ([contact]) will assist with the statistical considerations.

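### Ten or more balance variables are tested for three effects each at an unadjusted 0.05, with no decisive test, so the chance of a false positive is substantial

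*Combined protocol and SAP*

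**What the plan says.** Three sections bear on what counts as a positive result, and they do not agree.

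- **Section 3.1** places the pressure mat, motion-capture gait and the Pediatric Balance Scale (PBS) together under "Primary Outcome Measures". Sway is recorded under two conditions, eyes open and eyes closed.
- **Section 3.2** has "Primary endpoints: Reduction in PBS total score by 3.7 points". It then lists sway and gait endpoints with no rank. Safety is the only endpoint called secondary.
- **Section 11.0** lists ten dependent variables: sway area, anteroposterior sway, mediolateral sway, six gait parameters and PBS total. A two-way repeated-measures ANOVA is to give group, time and interaction effects. One rule covers all of them: "Statistical significance will be declared if" p is 0.05 or less, two-tailed.

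The sample size is not tied to one variable or one effect. Section 11.0 states "we predict the medium effect size (f=0.25) to detect significant changes within groups, between groups and effect of timepoint", and then "14 subjects in each group to have 0.8 power to detect this effect (alpha 0.05". The first hypothesis in section 2.1 is that VR gaming "will lead to increased postural control, as reflected by improved static and dynamic balance", which names no variable.

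**The concern.** Nothing in the plan says which variable, or which of the three effects, decides whether H1 or H2 is supported. Each test carries its own 5% error, and there are at least ten for the interaction alone. One chance result on, say, step width or mediolateral sway could therefore be reported as improved balance from VR, and the plan would give no ground for discounting it.

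The same threshold also covers the main effect of time. Both arms train balance for six sessions, so both may improve. A significant time effect says nothing about VR against traditional exercises, which is the comparison both Specific Aims name. The group main effect is a poor guide too, because it averages in the baseline visit, before any training.

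**Working it through.** **1. The plan's own sample size.** Inputs from section 11.0: f = 0.25, alpha 0.05, power 0.80, 14 per group. From section 7.0: three assessment visits (pre, post, 4-week retention). The documents do not give the correlation between visits or a sphericity correction; I assume 0.5 and none.

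For the group-by-time interaction with N participants and m visits:
- noncentrality = N × f² × m / (1 − rho)
- degrees of freedom = (m − 1) and (N − 2)(m − 1)

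With N = 28 and m = 3, the noncentrality is 28 × 0.0625 × 3 / 0.5 = 10.5, on 2 and 52 df. Power is 0.81, and 28 is the smallest even N that reaches 0.80. So 14 per group reproduces as one interaction test on one variable at an unadjusted 0.05.

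**2. Number of tests.** Section 11.0 gives 3 + 6 + 1 = 10 variables. If the two eye conditions are analysed separately, the sway variables double and the count is 6 + 6 + 1 = 13. Section 11.0 does not say which applies.

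**3. Chance of at least one false positive, interaction only, if VR adds nothing.** Under independence it is 1 − 0.95^k. For correlated variables I took k normal statistics with a common correlation r, each tested two-sided at 0.05. The documents give no correlations, so r is an assumption shown over a range.

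| Variables | Independent | r = 0.3 | r = 0.5 | r = 0.7 | r = 0.9 |
|---|---|---|---|---|---|
| 10 | 0.40 | 0.35 | 0.29 | 0.21 | 0.13 |
| 13 | 0.49 | 0.42 | 0.33 | 0.24 | 0.14 |

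A simulation of the mixed ANOVA itself (20 per arm, three visits, 6,000 runs) agrees to within about 0.02.

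**4. If the group main effect also counts as success.** In the same simulation, ten variables give 0.59, 0.51 and 0.39 at r = 0.3, 0.5 and 0.7.

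**5. Power of one named interaction test at 0.05** (formula in step 1, rho = 0.5).

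| Analysed N | Three visits | Baseline to session 8 only |
|---|---|---|
| 28 | 0.81 | 0.72 |
| 34 | 0.89 | 0.81 |
| 40 | 0.94 | 0.87 |

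The three-visit result depends on the assumed correlation. At rho = 0.3 power is 0.66 at N = 28 and 0.83 at N = 40. At rho = 0.7 it is 0.96 at N = 28.

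**The case against.** The best reply is that a primary endpoint already exists. Section 3.2 names PBS total, and both Specific Aims are comparative, so a sensible analyst would look first at the PBS interaction. The documents also nowhere say that one significant variable proves a hypothesis, and H1 is worded as static and dynamic balance together. This has force, but it does not control error. Section 3.1 contradicts the label and section 11.0 does not use it. Nor is the label usable as it stands: section 3.1 says a higher PBS score is better, while section 3.2 sets a reduction as the endpoint.

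Direction is a second fair point. The figures in step 3 count chance results either way, and section 3.2 gives an expected direction for most variables. Counting only favourable results under independence gives roughly 1 − 0.975^10 = 0.22, or 1 − 0.975^13 = 0.28. These are approximate, because the three-visit interaction has 2 degrees of freedom. Section 3.2 also lists only eight variables; 1 − 0.95^8 = 0.34.

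Some stronger readings are tempting, but the documents do not support them:

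- **That the plan tests thirteen variables.** It lists ten. Thirteen needs an analysis by eye condition that section 11.0 does not specify.
- **That the error is 0.86**, from 1 − 0.95^39 for thirteen variables and three effects. This treats every time effect as a false positive, yet a time effect may be real in both trained arms.
- **That a false positive is likely.** For the interaction alone, every scenario is below one half.
- **That any one significant variable counts as success by rule.** The text permits that use but does not state it. The defect is silence on the decision rule.

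**Conclusion.** The point stands. Section 11.0 applies one unadjusted threshold to at least ten variables and three effects, and the sections that could set a hierarchy disagree. For the relevant effect, the interaction, the chance of at least one false positive is about 0.21 to 0.40 for the ten listed variables, over correlations from 0.7 down to independence. For thirteen it is 0.24 to 0.49. Independence is the upper case, since step length, stride length, cadence and velocity are related. Even at a correlation of 0.9 the figure is 0.13 or 0.14, well above 0.05.

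That is a substantial inflation, and the conclusion does not depend on the count or on the assumed correlation. The absence of any adjustment or order is plain in the text. What remains uncertain is the exact size, and how the investigators would use the results.

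**What to change.** Change sections 3.1, 3.2 and 11.0 before the data are analysed.

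1. **One primary variable.** Name PBS total, already the primary endpoint in section 3.2. First reconcile section 3.1 with section 3.2 on the direction of a good result.
2. **One confirmatory test.** Make it the three-visit group-by-time interaction at 0.05. This matches the stated 14 per group, and "total 40 participants are being recruited", so up to 12 can be lost before N falls to 28. If the baseline-to-session-8 contrast is preferred, say that power at N = 28 is 0.72 and that 34 analysed participants are needed for 0.80; tolerable loss then falls to 6.
3. **Eye conditions.** State how the two enter the analysis.
4. **All sway and gait variables secondary.** Report them as estimates with 95% confidence intervals and no significance claims. Alternatively, test them with one Holm procedure across all of them, only after the primary test succeeds. Separate Holm families for static and dynamic balance beside the primary test would leave three families at 0.05 each, with overall error up to 1 − 0.95³ = 0.14 if independent.
5. **Main effects.** State that the time main effect, and the group main effect averaged over baseline, are not evidence for VR.

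The cost is wording, with no extra participants or measurements. The price is that secondary significance claims are given up or become harder: the first Holm step is 0.05/9 = 0.0056 for nine sway and gait variables, or 0.05/12 = 0.0042 for twelve. The three-visit test also does not show at which visit the arms differ, so the between-arm difference in change at sessions 8 and 9 should be reported beside it.

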# 12.0 Data Management

Qualisys motion capture system, visual 3D and HR mat use the inbuilt software for collecting and cleaning the data. HR mat data will be exported to MATLAB for analysis of postural sway. The data will be stored on an access-controlled computer situated in laboratory 70 E of the School of Public Health building in Indiana University Bloomington. Only approved study personnel will have access to this data.

## 13.0 Privacy/Confidentiality Issues

Participants will be recruited through flyers posted in the community and various Indiana University Buildings. Subjects will be assessed in the private setting of Physical activity and Biomechanics labs in the School of Public Health building. Informed consent form will be obtained from the subjects prior to the research procedure online via Qualtrics. All phone conversations regarding the consent/ assent process will occur in the private setting of the researcher's office behind the closed doors. The intervention will take place at participants own home ensuring privacy. All the data collected for this study will be placed in a locked cabinet in laboratory 70 E of the School of Public Health building in Indiana University Bloomington. The only people that will access this information are approved study personnel.

# 14.0 Follow-up and Record Retention

Session numbers 8 and 9 will be follow-up and retention assessment sessions. Session 8 will occur 3-5 days after the last intervention day and session 9 will occur 4 weeks after the last day of intervention. The data will be retained for 3 years after the end of the study.

# 2. ASSQ:

# **Autism Spectrum Screening Questionnaire (ASSQ)**

Please read the statement below and indicate by answering, No, Somewhat, or Yes if this your child/you stands out as different from other children/adults of his/her age in the following ways:

		No	Somewhat	Yes
		0	1	2
1	is old-fashioned or precocious			
2	is regarded as an "eccentric professor" by the other children			
3	lives somewhat in a world of his/her own with restricted			
	idiosyncratic intellectual interests			
4	accumulates facts on certain subjects (good rote memory)			
	but does not really understand the meaning			
5	has a literal understanding of ambiguous and metaphorical			
	language			
6	has a deviant style of communication with a formal, fussy,			
	old-fashioned or "robotlike" language			
7	invents idiosyncratic words and expressions			
8	has a different voice or speech			
9	expresses sounds involuntarily; clears throat, grunts,			
	smacks, cries or screams			
10	is surprisingly good at some things and surprisingly poor at			
	others			
11	uses language freely but fails to make adjustment to fit			
	social contexts or the needs of different listeners			
12	lacks empathy			
13	makes naïve and embarrassing remarks			
14	has a deviant style of gaze			

15	wishes to be sociable but fails to make relationships with		
	peers		
16	can be with other children but only on his/her terms		
17	lacks best friend		
18	lacks common sense		
19	is poor at games: no idea of cooperating in a team, scores		
	"own goals"		
20	has clumsy, ill coordinated, ungainly, awkward movements		
	or gestures		
21	has involuntary face or body movements		
22	has difficulties in completing simple daily activities because		
	of compulsory repetition of certain actions or thoughts		
23	has special routines: insists on no change		
24	shows idiosyncratic attachment to objects		
25	is bullied by other children		
26	has markedly unusual facial expression		
27	has markedly unusual posture		

# 3. Screening Questionnaire (Qualtrics survey)

# Screening questionnaire: Effect of virtual reality-based training on postural control in youth with autism spectrum disorder (ASD)

Q1	Name of the participant:
Q2	2 Do you have any of the following documents confirming autism diagnosis:
	Document provided by the physician (1) School services categorized under ASD (2) Seeking therapeutic services categorized under ASD (3) Any other official documents indicating the diagnosis of ASD, please specify: (4)
reg o	Will you be willing to provide researcher with a copy of those document under HIPPA safety gulations?  Yes (1)  No (2)
	Poes participant currently receive any medications?  Yes (1)
	No (2) If yes, please mention the medications: (3)

Q5 Does the participant currently have any of the following musculoskeletal conditions?

	Yes (1)	No (2)
Joint or muscle pain or stiffness that limits mobility (1)	0	0
Fractures or recent surgeries (2)	0	0
Implanted plates, pins, or screws that limit mobility (3)	0	0
Any other physical condition that could interfere with the ability to play an active video game (4)	0	0

Q6 Does participant currently have any of the following neurological symptoms?

	Yes (1)	No (2)
Numbness or muscle weakness (1)	0	0
Temporary loss of vision, speech or strength (2)	0	0
Loss of consciousness (black out) (3)	0	0
Dizziness or lightheadedness (4)	0	0
Impaired memory or confusion (5)	0	0
Epilepsy or seizures (6)	0	0
Any other cooccurring diagnosis that could be negatively impacted by playing an active video game (7)	0	0

Q7 Does participant currently have any of the following symptoms?

	Yes (1)	No (2)
Uncorrected vision loss or any other eye condition prohibiting looking at the screen for a prolong time (1)	0	0
Impaired hearing (uncorrected) (2)	0	0
Medically documented balance disorder (3)	0	0
Any heart condition prohibiting exercise (4)	0	0
Chronic pain or any pain at the time of testing (5)	O	0
Aggression or other severe behaviors that may limit the ability to safely participate in this study (6)	0	0
Assistance to stand for 20 minutes or more (7)	0	0

Q8 Does participant currently receive physical or occupational therapy specifically for improving balance?

- o Yes (1)
- o No (2)

Q9 Has participant received physical or occupational therapy in the past specifically for improving balance?

- o Yes (1)
- o No (2)

	0 Do you perceive participant having any challenges with balancing self such as frequent
	pping while walking, frequent falls, uses support while walking or standing unsupported?  Yes (1)
	No (2)
	If yes, please specify: (3)
Q1	1 Does participant currently play any video games?
0	Yes (1)
	No (2)
0	If yes, specify the gaming consoles: (3)
Q1	2 What the frequency of playing the video games?
	3 Does participant currently play active video games (which involves participant moving his dy to move the avatar on the screen)?
0	Yes (1)
0	No (2)
0	If yes, what is the frequency and average duration: (3)

Q14 Does participant currently have access to Nintendo Switch Sports (2022) game  O Yes (1)  O No (2)	e?
Q15 Does participant have any other challenges that may limit their ability to engage study such as will he/she be able to engage in video game activity for 10 minutes with distracted?	=
	<del>-</del>
Q16 Will the participant need any individualized motivation such as visual schedul sticker chart, etc. for engaging in this research? Please specify:	e, checklist,
	_

### 6. Edinburgh Handedness Inventory-short form

## **Edinburgh Handedness Inventory - Short Form**

Please indicate your preferences in the use of hands in the following activities or objects:

	Always right	Usually right	Both equally	Usually left	Always left
Writing					
Throwing					
Toothbrush					
Spoon					

## 7. Pediatric Berg's Balance Scale:

### Pediatric Balance Scale

	r caratire Bararice Scare
1	Seated position to standing position
2	Standing position to sitting position
3	Transfer
4	Standing without support
5	Sitting without support
6	Standing with eyes closed
7	Standing with your feet together
8	Standing with one foot in front
9	Standing on one foot
10	Rotating 360 degrees
11	Turning to look back
12	Picking up an object off the floor
13	Placing alternate foot on step / footrest
14	Reaching forward with extended arm
